3.1. Study design

Randomized triple-blinded multicentric clinical trial, conducted in parallel, with two arms:

The trial will be performed with health care workers (Physicians, Nurses, Respiratory therapists, or nurse assistants) free of SARS-CoV-2 infection prior, recent or at the time of the inclusion and who directly care for confirmed or suspected cases of COVID-19 in the emergency room, general COVID wards or intensive care units. A screening at baseline will be carried out in order to evaluate for eligibility by performing: SARS-CoV-2 RT-PCR, SARS-CoV-2 IgG antibodies, as well as, hemogram, creatinine, serum phosphorus, AST, ALT, ELISA for HIV, surface Hepatitis B antigen antibodies, qualitative pregnancy test (b-HCG). Once

eligibility is verified participants will be randomly assigned to either an intervention or a control group.

The interventions consists in the administration of Tenofovir/ Emtricitabine (300 mg / 200 mg daily during 60 days) + Personal Protective Equipment (PPE) and the control consists in the administration of placebo (1 tablet daily during 60 days) + Personal Protective Equipment (PPE)

All participants will have PPE recommended for the preventions of COVID-19 by the WHO which include mayo dress, nonfluid long sleeve gown, ocular protection with goggles, face shield or visor and surgical mask in procedures that do not aerosolize. N-95 respirators are required for procedure that generate aerosols. For detailed description see Table 2.

The re-use of N-95 respirators will be allowed according to CDC and WHO guidelines. This taking into consideration the shortage of supplies for the actual situation. The N-95 continuous use will be for 8 hours and the N-95 intermittent use will be allowed up to 5 times with the precaution of storage in a paper and plastic bag label them with the participant name and placed them in a plastic recipient at the end of shifts(48).

After baseline evaluation and confirming eligibility an initial visit and 4 follow up visits at day 20, 40, 60, 75 days will be carried out. See Table 1 and Graph 1.

In the case of presenting COVID-19 related symptoms at any time after enrolling a SARS-CoV2 RT-PCR will be performed between day 1 to 5 of the onset of symptoms and will be repeated it after 72 hours in case that the first one is negative. In the case of having any positive SARS-CoV2 RT-PCR or SARS-CoV2 IgG SARS-CoV2 infection will be confirmed and the intervention will be suspended.

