3.6.9 Study withdrawal criteria

The following criteria should determine the immediate withdrawal of the volunteer from the study:

- Grade 2 or greater kidney abnormalities at any time of follow-up.
- Clinical indication to start a drug with significant interactions with TDF/FTC during the development of the study.
- Presentation of any serious adverse event related to the intervention, defined by the physicians assigned to the study.
- Any Adverse Event (AE) that determines that the volunteer wishes to interrupt the intervention.
- That the volunteer voluntarily and for any reason decide to withdraw from the study.

If any of the previously mentioned criteria are met, the doctor assigned to the study in charge of the follow-up will immediately inform the coordinator of their respective center. The report of all AE will be made by the principal investigator of each center, in accordance with the INVIMA regulations and taking into account the Standardized Operating Procedures (SOP) established by the study.

In the event that the patient withdraws their consent, no additional monitoring will be possible. This situation will be reported immediately to the clinical monitor and monthly to the Institutional Research and Ethics Committee (CIEI).

3.6.10. Follow-up of volunteers with a positive pregnancy test at the end of follow-up

Despite the fact that TDF/FTC is a classification B drug in pregnancy, and its use is recommended as one of the antiretrovirals of choice in pregnant women with HIV (76), within this study it was defined to exclude pregnant women, or with the desire to become pregnant, to avoid exposure to this drug given its high placental transfer to the fetus.

There is no evidence in humans of teratogenicity with TDF/FTC, however there is evidence in monkeys, at doses twice as high as the therapeutic doses in humans, of decreased fetal growth and reduced fetal bone porosity within two months of initiation of maternal therapy; Regarding human studies, there is no demonstrated relationship with low birth weight, but there are conflicting results on the outcome of growth in childhood (77).

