In a randomized, double-blind, placebo-controlled trial of PrEP in African women, Mugo NR, and colleagues (78) evaluated the effect of TDF/FTC on pregnancy for HIV-uninfected women. Differences in the incidence of pregnancy, delivery outcomes, and infant growth were not statistically different for women who received PrEP with TDF alone, or combination of FTC + TDF compared to placebo at conception. Considering that PrEP was discontinued when pregnancy was detected and that the confidence intervals for delivery outcomes were wide, the authors did not commit to making definitive statements about the safety of PrEP in the period of periconception (78).

For the above reasons, if any volunteer presents a pregnancy at the end of the intervention period, a specific Informed Consent Form will be filled out to carry out a follow-up during the pregnancy.

4. Statistical analysis plan

Initially, a descriptive analysis of the information will be made, and measures of central tendency and dispersion will be reported according to the type of variables. In this phase, the similarity between the groups of the experiment will be evaluated and it will be calculated if there are differences in the groups due to chance.

Primary outcome

Taking into account that this study is a pragmatic clinical experiment, which will evaluate effectiveness, an intention-to-treat analysis will be carried out, to solve the main objective, the proportion of incidence of SARS-CoV-2 infection in each group will be determined at the day 75 post-randomization, estimated as the cumulative incidence of infection using the Kaplan Meier method.

Exposure of interest: Prophylaxis with TDF/FTC plus EPP vs placebo plus EPP.

Primary outcome: SARS CoV2 infection

Zero follow-up time (registration time in the registry): the time that the volunteer is randomized to the study interventions.

Follow-up time: All individuals have a follow-up until they present the primary outcome, or meet any of the withdrawal criteria, or up to 75 days after the zero follow-up time, if they do not present the outcome.

Event: SARS-CoV-2 infection.

Censorship: censorship occurs when the outcome is not presented, the two types of censorship will be: administrative censorship 75 days after randomization, or censorship for compliance with any of the criteria for withdrawal from the study, or loss of follow-up.

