Withdrawal of investigational product	Qualitative/nominal	Decision by investigator or patient to withdraw investigational product before planned.	0-Not applicable 1- Withdrawal due to kidney dysfunction. 2- Withdrawal due to need for new interacting medications. 3- Withdrawal due to development of any SAE deemed to be related to intervention. 4- Withdrawal due to any AE that makes the volunteer decide to interrupt investigational product. 5-Voluntary withdrawal.
Date of investigational product withdrawal	Quantitative/continuous	Date of discontinuation of investigational product, only if previous answer was other than 0	Day/month/year
Time to discontinuation of investigational product	Quantitative/discrete	Time between initiation of investigation product to discontinuation	Number of days
Severity of COVID-19	Qualitative/nominal	Classification of severity as follows: - Asymptomatic infection - Mild disease: defined as not requiring hospitalization. - Moderate disease: defined as requiring hospitalization outside of the ICU. - Severe disease: defined as requiring hospitalization in ICU.	1-Asymptomatic 2-Mild 3-Moderate 4-Severe
Date of hospitalization start	Quantitative/continuous	Date of hospitalization start	Day/month/year
Date of hospital discharge	Quantitative/continuous	Date of hospital discharge	Day/month/year
Date of ICU admission	Quantitative/continuous	Date of ICU admission	Day/month/year
Fecha de egreso del UCI	Quantitative/continuous	Date of ICU discharge or date of death	Day/month/year
Date of recovery from COVID-19	Quantitative/continuous	Recovery from COVID-19 defined as a minimum of 10 days after symptom start plus at least 72 hours of symptom improvement. If the patient died, record 00/00/00	Day/month/year
Final status	Quantitative/continuous	Record of volunteer status at the end of follow-up	0- Death 1- Alive
Date of end of follow-up	Quantitative/continuous	Date of end of follow-up	Day/month/year

References

1. Daihai H, Daozhou G, Zhuang Z, Peihua C, Yijun L, Lin Y. The attack rate of the COVID-19 in a year. :3–5.

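### The primary analysis is called intention-to-treat, but follow-up stops and participants are censored at withdrawal criteria that are mostly about the product, so infections not yet confirmed can be lost

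*Combined protocol and SAP*

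**What the plan says.** Section 4 (Primary outcome) calls the trial pragmatic and states that "an intention-to-treat analysis will be carried out", with cumulative incidence at day 75 by Kaplan-Meier and a hazard ratio from a Cox model. The follow-up definition beneath it says "All individuals have a follow-up until they present the primary outcome, or meet any of the withdrawal criteria", or until day 75. The censoring definition includes "censorship for compliance with any of the criteria for withdrawal from the study", besides day 75 and loss to follow-up.

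Section 3.6.9 (Study withdrawal criteria) makes each criterion a cause of immediate withdrawal from the study. The five are:
- a kidney abnormality of grade 2 or more;
- "Clinical indication to start a drug with significant interactions with TDF/FTC during the development of the study";
- a serious adverse event related to the intervention;
- "Any Adverse Event (AE) that determines that the volunteer wishes to interrupt the intervention";
- the volunteer's own decision to leave.

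The same section rules out further observation in one case only: "In the event that the patient withdraws their consent, no additional monitoring will be possible". Appendix 3 codes the same reasons under a variable defined as "Decision by investigator or patient to withdraw investigational product before planned", that is, as stopping the product.

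**The concern.** An intention-to-treat analysis counts outcomes in everyone as randomised, whether or not they stay on product. Under this rule, time after a product-related withdrawal is removed, so for these participants the analysis is on-treatment.

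Infection is also confirmed with a delay. Section 3.1 says a "SARS-CoV2 RT-PCR will be performed between day 1 to 5 of the onset of symptoms and will be repeated it after 72 hours" if the first result is negative, and antibodies follow at day 14 from symptom onset if RT-PCR stays negative. No SARS-CoV-2 test is scheduled between baseline and day 40. A participant who meets a criterion inside that delay leaves as uninfected.

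Kaplan-Meier and Cox assume that censoring is unrelated to infection risk. Here it may be related. Appendix 2 bars antibiotics such as clarithromycin, which could be started for an early respiratory illness. Fatigue and diarrhoea are both COVID-19 trigger symptoms (Section 3.6) and effects reported in the cited trials of regimens containing the drug (Section 5.1.1). Tests not done after withdrawal cannot be recovered at analysis.

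**Working it through.** **1. The plan's own figure.** Inputs from Section 3.4: risks 0.10 and 0.05, power 0.80, alpha 0.05 (two-sided assumed), 1:1.
- Pooled formula: n per group = [1.96·√(2·0.075·0.925) + 0.842·√(0.10·0.90 + 0.05·0.95)]² / 0.05² = 435. The unpooled version gives 432. The plan's 429 agrees within 3%.
- Inflation for 10% loss: 858/0.90 = 954 after rounding up, against 950 in the plan.

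The sample size is not in dispute.

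**2. Events and power at the planned risks.**
- Events: 475 × 0.10 + 475 × 0.05 = 71.25.
- Hazard ratio implied by the risks: ln 0.95 / ln 0.90 = 0.487.
- Schoenfeld power: Φ(½·√d·|ln HR| − 1.96).

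| Equal loss of infections | Events d | Schoenfeld power | Simulated Cox (Wald) power |
|---|---|---|---|
| 0 | 71.25 | 86% | 83% |
| 10% | 64.1 | 82% | 79% |
| 20% | 57.0 | 78% | 75% |

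**3. Bias when loss differs by arm.** If a share L of infections is lost in each arm, observed HR ≈ true HR × (1 − L active)/(1 − L placebo). The losses below are assumptions.

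| Loss, active v placebo | Multiplier | True HR 1.0 becomes | True HR 0.487 becomes |
|---|---|---|---|
| 10% v 5% | 0.90/0.95 = 0.947 | 0.95 | 0.46 |
| 15% v 5% | 0.85/0.95 = 0.895 | 0.90 | 0.44 |
| 5% v 15% | 0.95/0.85 = 1.118 | 1.12 | 0.54 |
| equal | 1.000 | 1.00 | 0.49 |

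A simulation (475 per arm, 75 days, 10% placebo risk, lost infections censored 1 to 14 days before confirmation, 3000 runs) gave null hazard ratios of 0.94, 0.90, 1.12 and 1.00. It checks the formula, not the assumed losses.

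**4. What the documents suggest about size.** Section 5.1.1 reports HIV prophylaxis studies only.
- In one trial, safety interruptions took 0.7% of follow-up time on TDF-FTC and 0.6% on placebo. Used illustratively as losses, the multiplier is 0.993/0.994 = 0.999.
- In the same trial, six subjects on tenofovir-containing arms stopped for raised creatinine and none on placebo: 6/(1,584 + 1,579) = 0.19%.
- In a cohort, 56 of 1,225 (5%) stopped for adverse effects, 22 of them temporarily, over a possible 1,784 person-years. At a constant rate this is 56/1,784 × 475 × 75/365 ≈ 3 volunteers per arm of 475 over 75 days, and more if stops cluster early.

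**5. Limits of the mechanism.** Creatinine is measured at days 40 and 60, when IgG and RT-PCR respectively are also taken, so a kidney withdrawal found there loses only later tests. Missed or lost tablets, and suspension for hospitalisation with high suspicion, are not withdrawal criteria.

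**The case against.** **Appendix 3 points both ways.** Its interruption variable has an adverse-event code recorded at visits 1 to 3, and its list of withdrawal criteria omits the adverse-event criterion. That suggests such participants may stay in follow-up. The interruption code fits temporary stops, however, and the omission does not override Sections 3.6.9 and 4. It adds one more inconsistency to reconcile.

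**An antibiotic started blind for early COVID-19 should remove a similar share of infections from each arm.** This stands unless the drug changes how illness presents. That route may cost power and leave the hazard ratio intact.

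**The documents' own rates are low.** This also stands. Losses of 15% v 5% have no support in the text and are illustrations only.

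**Testing may continue anyway.** Section 3.6 offers RT-PCR for symptoms at any time after randomisation and a day-60 RT-PCR for all participants. But the symptom rule applies during follow-up, which Section 4 ends at the criterion, and a later positive would fall outside the analysis.

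**Following everyone dilutes the effect.** Suppose 10% v 5% withdraw evenly over days 0 to 60, and that after stopping, the hazard in either arm is 1 to 3 times the control level. The risk ratio to day 75 then moves from 0.50 to between 0.530 and 0.606, and two-proportion power at 475 per arm falls from 0.834 to between 0.778 and 0.633. The cost is real under those assumptions, but that diluted effect is the one an intention-to-treat analysis is meant to estimate.

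**Conclusion.** The concern holds and needs correcting. Section 4 does not deliver the analysis it names: it censors at product-related reasons although Section 3.6.9 rules out monitoring only when consent is withdrawn. No outcome testing after the other withdrawals and no sensitivity analysis for informative censoring is described.

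The contradiction in the text is certain. The size and direction of any bias are not, because the documents give no withdrawal rates for this trial. Bias is near nil if withdrawal is rare or the loss is balanced, and about 5% to 12% on the hazard ratio under the assumed unequal losses. The plan's 10% inflation roughly preserves the intended 80% power at 10% equal loss (82% by Schoenfeld, 79% simulated). It gives no protection against bias.

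**What to change.** Leave the rules for stopping the product as they are, and separate stopping the product from leaving the study.
- Follow every randomised participant to day 75, with scheduled and symptom-triggered tests, unless consent is withdrawn or contact is lost. Count those infections in the primary analysis as randomised.
- Censor only at consent withdrawal, loss to follow-up or day 75.
- Keep the present censoring rule as a prespecified sensitivity analysis.
- Report withdrawals by arm and reason, using the Appendix 3 codes.
- Reconcile Section 3.6.9, Section 4 and Appendix 3 on which events end follow-up. Also reconcile Section 3.2 with Appendix 2, which differ on whether short use of the listed anti-inflammatory drugs counts as barred.

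The cost is protocol and SAP wording plus continued contact with, and testing of, participants who are off product. Section 9.1 already budgets the follow-up 2 tests for 950 volunteers and the end-of-treatment RT-PCR for all subjects. The possible dilution of the effect should be acknowledged when power is discussed.

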3.3. Result and primary Outcome

Primary Outcome

✓ SARS-CoV-2 infection defined as:

- Detection of SARS-CoV-2 nucleic acid using RT-PCR in any of the specimens collected during the study-follow-up including the asymptomatic participant

-Positive IgG antibodies against SARS-CoV-2 in any of the specimens collected during the study-follow-up

Secondary outcomes

- Serious and non-serious adverse events

- Discontinuation of using the intervention (TDF/FTC or placebo) for any reason

- Adherence to TDF/FTC defined as: number of tablets taken/total number of dispensed tablets

- Severity of SARS-CoV-2 infections according to the following categories:

[figure not shown]
- Asymptomatic infection.

- Mild symptomatic SARS-CoV-2 infection with no need for hospitalization.

- Moderate symptomatic SARS-CoV-2 infection that requires hospitalization, but no ICU.

- Severe SARS-CoV-2 infection: dyspnea with other SARS-CoV-2 symptoms requiring ICU hospitalization.

Graph 1. Flowchart of assignments and follow up of the clinical trial.

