3.6.5. Administration of the intervention product and placebo

Volunteers assigned to the intervention group will receive one tablet of TDF/FTC 300/200mg each day. Each volunteer will be given 60 tablets of the medicine at the beginning of the treatment and its administration will be verified daily by sending a virtual survey, in which the subject answers if he took the intervention, plus a follow-up diary that will be given to the patient of Virtual or manual way for people without access, to write adverse events, as well as the hours of daily exposure to patients with suspected or diagnosed COVID 19 and adherence to personal protection elements. These data will be stored in an eCRF for clinical follow-up, adverse events, and adherence.

Patients assigned to the control group will receive a placebo that will have the same appearance and size and will not have any active ingredients. Similarly, 60 placebos will be delivered from the start of treatment.

The medicine must be stored at a temperature not exceeding 30 ° C and in an environment without excessive humidity in its authorized container and packaging.

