The hazard ratio will be estimated by comparing the risk of infection in the intervention group (TDF/FTC + EPP), with the risk in the control group (placebo + EPP), with a confidence interval of 95 %, using a univariate Cox regression model.

If necessary, adjustment will be made for variables that may affect the occurrence of the primary outcome and that are not balanced between the intervention group and the placebo group; The need for adjustment with an OR greater than 1.5 will be considered for dichotomous categorical

variables, such as sex; or if there are differences between the groups greater than 0.25 of the standard deviation for continuous variables such as age, adherence to pharmacological intervention or EPP, and hours of exposure to the COVID area. For the calculation of the adjusted hazard ratio, a multivariate Cox proportional hazards model will be used, if the proportionality assumption is met, or an extended Cox model if this assumption is not met.

For secondary outcomes

-The proportion of incidence of total adverse effects in each group will be determined at day 60 after randomization, estimated as the cumulative incidence using the Kaplan Meier method.

The hazard ratio ("Hazard Ratio") will be estimated by comparing the risk of adverse events in the intervention group (TDF/FTC + EPP), with the risk in the control group (placebo + EPP), with a confidence interval of 95%, using a univariate Cox regression model.

Additionally, the same analysis will be performed for serious adverse events.

- The proportion of incidence of discontinuation of the intervention in each group, for any reason, will be determined at day 60 after randomization, estimated as the cumulative incidence using the Kaplan Meier method.

The hazard ratio will be estimated by comparing the discontinuation of the intervention in the intervention group (TDF/FTC + EPP), with the risk in the control group (placebo + EPP), with a confidence interval of 95 %, using a univariate Cox regression model.

- It will be determined as the difference in the mean or median (according to the distribution of the data) of the percentage in which the individuals were adherent

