Nausea	Qualitative/nominal	A feeling of sickness featured by an urge to vomit.	1-Grade 1 2-Grade 2 3-Grade 3
Headache	Qualitative/nominal	Headache	1-Grade 1 2-Grade 2 3-Grade 3
Abdominal pain	Qualitative/Nominal	A feeling of distress or pain in abdominal area.	1-Grade 1 2-Grade 2 3-Grade 3
Flatulence	Qualitative/nominal	A disorder highlighted by abnormally increased gas discharge by lower gastrointestinal tract.	1-Grade 1 2-Grade 2
Insomnia	Qualitative/nominal	A disorder characterized by difficulty to start or maintain sleep.	1-Grade 1 2-Grade 2 3-Grade 3
Vomit	Qualitative/nominal	A disorder featured by a reflex act or actively regurgitating stomach contents through mouth	1-Grade 1 2-Grade 2 3-Grade 3 4-Grade 4 5-Grade 5
Maculopapular skin rash	Qualitative/nominal	A disorder featured by the appearance of macules and papules. Also known as morbilliform eruption. Often associated with pruritus.	1-Grade 1 2-Grade 2 3-Grade 3
Steven-Johnson's syndrome	Qualitative/nominal	A disease in which at least 10% of body surface area develops a severe sphenelating lesions and bullae, also compromising mucosal membranes.	3-Grade 3 4-Grade 4 5-Grade 5
Allergic reaction	Qualitative/nominal	A disorder featured by a local or diffuse skin reaction upon exposure to an allergenic.	1-Grade 1 2-Grade 2 3-Grade 3 4-Grade 4 5-Grade 5
Other allergic reaction	Qualitative/nominal	Se coloca la clasificación de la reacción alérgica reportada según la	1-Grade 1 2-Grade 2 3-Grade 3 4-Grade 4 5-Grade 5
Adherence by tablet count	Qualitative/discrete	Number of drug/placebo tablets taken to follow-up date	Number of tablets
Drug/placebo interruption	Qualitative/dichotomous	Any interruption of investigational product	0- No 1- Yes
Days of product interruption	Quantitative/discrete	Days of drug interruption	Number of days
Cause of drug interruption	Qualitative/nominal	Reason of drug interruption	1- Omission 2- AE 3- Accidental los of drug/placebo 4- Non-availability of drug/placebo
Additional data to be collected in Follow-up 2 and 3			

Temperature	Quantitative/continuous	Body temperature in Celsius degrees	Temperature in Celsius degrees
Heart rate	Quantitative/discrete	Heart rate	Heart rate in beats per minute
Respiratory rate	Quantitative/discrete	Respiratory rate	Respiratory rate in respirations per minute
Systolic blood pressure	Quantitative/discrete	Systolic blood pressure	Systolic blood pressure in mmHg

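### The adjusted primary hazard ratio may include adherence, which arises after randomization and is lowered by the infection itself, and the plan does not say which hazard ratio decides

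*Combined protocol and SAP*

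**What the plan says.** Section 4 (Primary outcome) states that "an intention-to-treat analysis will be carried out". It estimates the hazard ratio with a univariate Cox model. If necessary, it adjusts for variables that may affect the outcome and are unbalanced between arms. The trigger is an odds ratio above 1.5 for dichotomous variables and a difference above 0.25 SD for "continuous variables such as age, adherence to pharmacological intervention or EPP, and hours of exposure to the COVID area". An extended Cox model is mentioned only in case proportionality fails; nothing says that adherence would enter as a time-varying covariate. Nothing says whether the univariate or the adjusted hazard ratio carries the conclusion.

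Section 4 gives no formula for adherence. Elsewhere the documents say:

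- Section 3.3: "Adherence to TDF/FTC defined as: number of tablets taken/total number of dispensed tablets".
- Section 3.6.5: "Each volunteer will be given 60 tablets of the medicine at the beginning of the treatment"; the placebo arm likewise receives 60.
- Appendix 3 records "Number of drug/placebo tablets taken to follow-up date". With 60 dispensed to everyone, this final count is the Section 3.3 ratio on another scale.
- Section 3.1, on any positive RT-PCR or IgG: "infection will be confirmed and the intervention will be suspended". Section 3.6.9 (procedure for the primary outcome) agrees, and Section 3.6 continues product while an RT-PCR result is awaited.

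PPE adherence has no defined score. It is a diary item in Section 3.6.5, "as well as the hours of daily exposure to patients with suspected or diagnosed COVID 19 and adherence to personal protection elements". Exposure hours appear there and also among the demographic variables in Appendix 3, so their timing is unclear.

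**The concern.** A covariate measured after randomization can be changed by treatment. This one is also changed by the outcome: confirmed infection before day 60 stops tablet-taking and caps the score. Entered as a fixed covariate, a low score then partly means infected, and the Cox model learns that low scorers have a high hazard. If the drug arm scores lower for another reason, such as intolerance or withdrawal, the model expects more infections there. An equal number of infections then looks like protection.

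The trigger adds to the problem. With 475 per arm a true baseline continuous variable almost never differs by 0.25 SD, so for continuous variables the rule fires almost only when something after randomization has moved the variable in one arm. Adjustment is least safe in that situation. At stake is a false finding of protection in a trial that Section 5.2 expects could change public policy for health personnel.

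**Working it through.** **1. The plan's own figure.** Section 3.4 uses risks of 0.10 and 0.05, alpha 0.05 (two-sided assumed) and 80% power. The pooled two-proportion formula gives 435 per group and the arcsine formula 424, which bracket the stated 429. The sample size is not in dispute. The implied hazard ratio is ln 0.95 / ln 0.90 = 0.487.

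**2. How infection lowers the score.** A participant who takes every tablet until confirmation on day t scores t/60: 20/60 = 33%, 40/60 = 67%, 60/60 = 100%. Scheduled tests are IgG on day 40, RT-PCR on day 60 and IgG on day 75 (Table 1), so confirmation before day 40 needs symptoms.

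**3. How often the trigger fires by chance.**
- Continuous baseline variable, 475 per arm: 2 × [1 − Φ(0.25/√(2/475))] = 0.00012.
- Sex, at the 80% women budgeted in Section 9.1: 2 × [1 − Φ(ln 1.5/√(2/(475 × 0.8 × 0.2)))] = 0.012.

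**4. Simulation with no drug effect.**
- From the documents: 475 per arm, 10% control risk by day 75, and censoring at withdrawal.
- Placebo tablet-taking of 92% borrows the pill-count figure in Section 5.1.1, which is not reported by arm there.
- Assumed: the gaps between arms, a between-person SD of tablet-taking of 0.08 or 0.15, and withdrawals spread evenly over days 0-60.
- Detection was either immediate (2,000 trials per scenario) or on the visit schedule (1,500 trials each with 50% and 70% symptomatic, assumed). Scheduled detection used confirmation 8.5 days after infection for symptomatic cases (5.5-day incubation from Section 1.3 plus 3 assumed) and 35% RT-PCR sensitivity at day 60 (Section 3.6 gives 30 to 40%).
- Rule: if tablets/60 differs by more than 0.25 pooled SD, the adjusted hazard ratio decides; otherwise the univariate one does.

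At equal 92% tablet-taking, the mean score was 0.92 in uninfected participants and 0.54 (immediate) or 0.65-0.69 (scheduled) in infected ones.

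Type I error at two-sided 5%; ranges span both detection models:

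| Drug vs placebo | SD 0.08 | SD 0.15 |
|---|---|---|
| Tablet-taking 90% vs 92% (trigger 0.5-6%) | 4-5.5% | 4-5.5% |
| Withdrawals 10% vs 5% (trigger 0.6-1.7%) | 4-5% | 4-5% |
| Withdrawals 15% vs 5% | 6.5-10% (trigger 21-31%) | 4-5% (trigger 12-18%) |
| Tablet-taking 88% vs 92% | 13-27% | 6-10% |
| Withdrawals 20% vs 5% | 17-32% | 8-12% |
| Tablet-taking 85% vs 92% | 67-75%, adjusted HR 0.56-0.59 | 18-32%, adjusted HR 0.74-0.85 |

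Monte Carlo error is about 0.5-0.7 points near 5% and up to 1.2 points at higher rates. If the univariate hazard ratio decides, it is 0.99-1.01 with 3.5-6% error in every row.

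**5. Sensitivity to the assumptions.** A second simulation (immediate detection) gave 56-61% and 13-14% for 85% vs 92% (SD 0.08 and 0.15), 10-11% and 5% for 88% vs 92%, and 28-30% and 11% for 20% vs 5% withdrawals. Another, with mean tablet-taking of 90%, gave 43% for 20% vs 5%. The direction is stable; the sizes are not.

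**6. Locating the cause.** With elapsed on-product days as denominator, error is 4-6% and the adjusted hazard ratio 0.99-1.01. In a control run where infection did not feed back into the score, adjustment was harmless (HR 0.99, 4.4% rejection). The distortion comes from the event lowering its own covariate.

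**7. A working drug.** With a true hazard ratio of 0.487 and equal adherence, power is 84-85% under either reading.

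**The case against.** The plan declares intention-to-treat, gives the univariate model first and unconditionally, and says only that the need for adjustment will be considered. A reader could fairly take the univariate hazard ratio as primary, and then this error does not reach the conclusion. An elapsed-days adherence percentage could also be built from the daily survey and the interruption fields, and it would remove the bias.

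The large gaps have thin support in Section 5.1.1. One PrEP review found no overall adverse-event difference from placebo. Safety interruptions in one trial were 0.7% vs 0.6% of follow-up time. In another cohort 34 of 1,225 takers (2.8%) stopped permanently for adverse effects, and digestive symptoms explained 7% (95% CI 4-11%) of suboptimal adherence. Applied roughly to an 8-point shortfall, that is 8 × 0.07 = 0.56 points, below the smallest adherence gap simulated. No bias is shown for PPE adherence or exposure hours; under blinding, if treatment does not affect them, they would trigger as rarely as age.

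Most of this stands, and it limits the expected size. The same section, however, reports more gastrointestinal effects and fatigue on active drug and links digestive symptoms to lower adherence, so a difference cannot be excluded. The objection also needs a deciding hazard ratio and a denominator that the plan does not state.

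**Conclusion.** The concern holds. The plan permits adjustment of the primary effect for post-randomization adherence, its only defined drug-adherence ratio falls when infection is confirmed before day 60, and no deciding hazard ratio is named. Confidence in that reading is high.

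The size is conditional on the adjusted hazard ratio deciding when the trigger fires and on the covariate being tablets/60 or the tablet count. Harm is then negligible if the arms adhere alike, small for mild gaps (4-5.5% error), and serious only for gaps that the documents neither establish nor rule out. The rows for 88% and 85% tablet-taking and for 20% withdrawals are stress tests, not forecasts. For PPE adherence and exposure hours the objection is one of principle and timing, with no bias quantified. This should be fixed before the analysis; it does not affect the sample size.

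**What to change.** - Name the unadjusted intention-to-treat Cox hazard ratio as the deciding estimate.
- Remove drug adherence, PPE adherence and diary-recorded exposure hours from every model of the primary effect.
- Report any adjusted hazard ratio as supportive, with a short prespecified list of baseline variables from Appendix 3. An example is age (1 coefficient), sex (1), profession (3) and declared daily exposure hours (1) if recorded at enrolment: 6 coefficients.
- Analyse adherence as its own outcome, with days scheduled up to infection or stopping as the denominator.
- Dropping the imbalance trigger for true baseline variables is optional.

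The cost is SAP wording only: no new data, visits or participants. The supportive list must stay short. The planning risks imply 475 × 0.10 + 475 × 0.05 ≈ 71 infections, or about 10 per coefficient over 7 including treatment. With 429 evaluable per arm, 429 × 0.15 ≈ 64, or about 9 each.

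The change does not address the "censorship for compliance with any of the criteria for withdrawal from the study, or loss of follow-up". In simulations with no drug effect, 20% vs 5% withdrawals, and withdrawal-prone participants at 1.5, 2 or 3 times the infection hazard, the unadjusted hazard ratio was 0.97, 0.93 or 0.89 (error 5-9%). That is a separate issue.
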